6.0 CLINICAL RESEARCH DESIGN

6.1 Clinical research design

< Clinical research design >

This is a multicenter, collaborative, randomized, open-label study designed to explore the effects of administration of omega-3-acid ethyl esters [2 g (2 g PO QD) or 4 g (2 g PO BID) for 8 weeks] on vascular endothelial function, as measured by FMD, in patients receiving a hydroxymethylglutaryl-coenzyme A (HMG-CoA) reductase inhibitor and have concurrent hypertriglyceridemia.

Considering the potential bias by factors that affect FMD between treatment groups, stratified allocation will be performed with fasting TG as a factor.

Research TREATMENT

(1) Study drug:

Omega-3-acid ethyl esters

(2) Dosage regimen

Omega-3-acid ethyl esters will be orally administered [2 g (2 g PO QD) or 4 g (2 g PO BID)] immediately after meal for 8 weeks in patients with hyperlipidemia .

(3) Duration of treatment:

8 weeks

Planned number of research subjects:

40 patients evaluable for the primary endpoint

2 g group: 20 subjects

4 g group: 20 subjects

Number of study sites:

5 to 10 institutions

< Duration of the treatment and number of visits of by subjects >

(1) Duration of treatment:

The duration of the treatment period is 8 weeks. Research subjects should visit the hospital at the time of informed consent at Visit 1 (Day-29 to Day -1 before the start of study drug) and from the start of study drug administration at Visit 2 (Day -15 to Day -1 from the start of study drug administration) to completion of study drug administration [Visit 4 (Week 8)].

CONFIDENTIAL

(2) Number of visits

Observation period: 1 visit

Treatment period: 3 to 6 visits

The FMD measurement during the treatment period will be performed by a physician or laboratory technician who completed the FMD measurement training. Therefore, only for the FMD measurement, subjects are expected to go to a testing laboratory other than the one they normally visit for examinations. In that case, a total of 3 visits for the FMD measurement will be added to the total of 3 visits for examinations from Treatment Period Visit 2 (Day -15 to Day -1 before the start of study drug administration) to Visit 4 (Week 8). Therefore, the number of visits during the treatment period will be a minimum of 3 and a maximum of 6.

[figure not shown]
Figure 6 (a) shows an outline of the clinical research design. Refer to Appendix A for schedule of examinations, observations, and assessments.

Figure 6.a Outline of clinical research design

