13.1.3.1 Analysis of primary endpoints

%FMD(fasting)

[Analytical method]

- 1) Summary statistics by treatment group (number of subjects, mean, SD, minimum value, maximum value, quartiles) and a two-sided 95% confidence interval for the mean will be calculated at each evaluation time point during the treatment period, and a diagram illustrating the change in the mean \pm SD will be prepared.
- 2) The change for each treatment group (Treatment Period Visit 3 or Visit 4 - Treatment Period Visit 2) will be calculated at each evaluation time point during the treatment period and the same analysis as in 1) will be performed.
- 3) Using fasting TG at the start of treatment, a stratified analysis on summary statistics by treatment group (number of subjects, mean, SD, minimum value, maximum value, quartiles) and a two-sided 95% confidence interval for the mean will be performed.

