13.3 Determination of the number of planned research subject

40 patients evaluable for the primary endpoint

(Omega-3-acid ethyl esters 2 g: 20 patients, Omega-3-acid ethyl esters 4 g: 20 patients)

Exploratory biomarkers will be measured only for the research subjects from whom blood is taken during the observation period after approval of the revised protocol (the 2nd edition) by the committee such as the IEC.

[Rationale for the number of planned research subjects]

The planned sample size is based on the feasibility to explore the effects of omega-3-acid ethyl esters on vascular endothelial function.

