3. ANALYSIS SET

- Full Analysis Set

The subjects who were randomized and given at least one dose of the study drug.

- Safety Analysis Set

The subjects who are given at least one dose of the study drug.

4. CONSIDERATIONS for ANALYSIS

- Confidence coefficient

95% (two-sided estimation)

- Display digit

[Mean, Confidence coefficient, Quartiles]

Round statistics off to the 1 digits lower than significant digits of the data.

[Standard Deviation]

Round statistics off to the 2 digits lower than significant digits of the data.

[Minimum and Maximum Values]

Display the data at the significant digits.

[Proportion, Percentage]

Round statistics off to 1 decimal places.

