7. EFFICACY EVALUATIONS

7.1. Primary Endpoint and the Analytical Methods

Analysis Set: Full Analysis Set

Analysis Variables: %FMD (fasting)

Visit: Start of Treatment Period, Treatment Period 4 week and 8 week

Stratification Factor: Fasting TG at Observation Period

[150<= - <200, 200<= - <500]

Analysis Methods: For the above analysis variables, the following analysis is performed.

- (1) Summary statistics by treatment group and a two-sided 95% confidence interval for the mean will be calculated at each visit during the treatment period, and a diagram illustrating the change in the mean \pm SD will be prepared.
- (2) The change for each treatment group (Treatment Period 4 week/8 week – Start of Treatment Period) will be calculated at each visit during the treatment period and the same analysis as in (1) will be performed.
- (3) Summary statistics using stratification factor and two-sided 95% confidence interval (CI) of mean value by visit will be calculated by treatment group.
- (4) Using stratification factor, the change for each treatment group (Treatment Period 4 week/8 week – Start of Treatment Period) will be calculated at each visit during the treatment period and the same analysis as in (3) will be performed.
- (5) Analyses same as (1) - (4) are performed, excluding subjects with missing of %FMD (fasting) data at any visit as sensibility analysis.

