10.1. Adjustments for Covariates

In the analysis for primary endpoint for Full Analysis Set, stratified analysis of %FMD (fasting) is performed with Fasting TG value ($150 \leq - < 200$, $200 \leq - < 500$) at the start of treatment as a layer. Details are described in 7.1 (3) and (4).

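### The arm-level changes in fasting %FMD are valid as raw means, but they leave the Visit 2 value and the allocation TG stratum unused, at a small cost in precision and in side-by-side reading of the doses

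*SAP*

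**What the plan says.** SAP 7.1 analyses fasting %FMD in the Full Analysis Set at three times: "Visit: Start of Treatment Period, Treatment Period 4 week and 8 week". Item (1) gives summary statistics and a two-sided 95% interval for the mean, by arm. Item (2) does the same for the change from the start of treatment, which "will be calculated at each visit during the treatment period and the same analysis as in (1) will be performed". Protocol 13.1.3.1 matches: "Summary statistics by treatment group (number of subjects, mean, SD, minimum value, maximum value, quartiles) and a two-sided 95% confidence interval". Neither document contains a model or an adjusted arm mean.

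The allocation factor appears in SAP 7.1(3) and (4), as separate summaries for fasting TG 150 to <200 and 200 to <500. SAP 10.1, the section on covariate adjustment, offers only this: "In the analysis for primary endpoint for Full Analysis Set, stratified analysis of %FMD (fasting) is performed with Fasting TG value". The stratum results are not recombined into an arm estimate.

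Protocol 6.1 gives the reason for stratifying: "Considering the potential bias by factors that affect FMD between treatment groups, stratified allocation will be performed with fasting TG as a factor". Both possible covariates exist before randomisation by design. Fasting TG at Visit 1 is inclusion criterion 2, and a Visit 2 fasting FMD of 0% is exclusion criterion 4.

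**The concern.** The arm-specific mean change is the trial's main result. Randomised arms share one expected baseline mean, and a raw change makes no use of that. An arm that happens to start low tends to show a larger rise, and one that starts high a smaller one. The protocol names imbalance between arms in factors affecting FMD as a worry, yet no reported arm mean corrects for it. With a sample size set by feasibility, precision cannot come from more patients, so information already collected is worth using. What is at stake is interval width, and how far a reader can trust the 2 g and 4 g changes when they are set beside each other.

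**Working it through.** **Inputs.** From Protocol 13.3: "Omega-3-acid ethyl esters 2 g: 20 patients, Omega-3-acid ethyl esters 4 g: 20 patients". From SAP section 4: two-sided 95% intervals. The basis of the sample size is "The planned sample size is based on the feasibility to explore the effects of omega-3-acid ethyl esters on vascular endothelial function", so there is no SD, effect size or power to reproduce. Assumed: the same SD, s, at baseline and follow-up, and a baseline to follow-up correlation ρ between 0.2 and 0.9.

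**1. Raw interval.** The SD of change is s√(2(1−ρ)). The half-width is 2.093/√20 = 0.468 times that SD (19 degrees of freedom). At ρ = 0.5 the SD of change equals s, so the half-width is about 0.47 s.

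**2. Variance with a common baseline mean.**
- Raw: 2(1−ρ)s²/20.
- Adjusted: (1−ρ²)s²/20 + (1−ρ)²s²/40. The second term allows for the pooled baseline mean being itself estimated.
- Dividing both by (1−ρ)s²/20 gives the ratio (1.5 + 0.5ρ)/2: 0.80, 0.875, 0.925 and 0.975 at ρ = 0.2, 0.5, 0.7 and 0.9.
- The square roots, which are the SE ratios, are 0.894, 0.935, 0.962 and 0.987. They are the limit before the cost of estimating the slope.

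**3. Intervals at 20 per arm.** I simulated 20,000 two-arm trials per ρ with normal data, even TG strata and no stratum effect. Three intervals for one arm's mean change were compared: raw with the arm's own SD; raw with the SD pooled over arms; and adjusted for baseline and stratum, with an SE that allows for a random baseline. Mean half-widths are in units of s; ratios use unrounded values.

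| ρ | Raw, own SD | Raw, pooled SD | Adjusted | Adjusted / pooled raw | Adjusted / raw |
|---|---|---|---|---|---|
| 0.2 | 0.585 | 0.569 | 0.516 | 0.906 | 0.882 |
| 0.5 | 0.461 | 0.450 | 0.426 | 0.949 | 0.924 |
| 0.7 | 0.358 | 0.348 | 0.340 | 0.976 | 0.949 |
| 0.9 | 0.207 | 0.201 | 0.202 | 1.003 | 0.974 |

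The covariates' own share is the fifth column: about 9%, 5%, 2% and 0% narrower. Pooling the variance gives the rest, about 2 to 3%. Coverage was about 95% for both the raw and the adjusted interval. The simulation used baseline and one follow-up visit, not the three-visit model proposed under the fix.

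**4. Chance imbalance.** The baseline difference between arms has SD s√(2/20) = 0.316 s. The fraction (1−ρ) passes into the difference of raw changes: 0.5 × 0.316 = 0.158 s at ρ = 0.5. For one arm against the pooled baseline it is 0.5 × s√(1/40) = 0.079 s. At ρ = 0.7 the two figures are 0.095 s and 0.047 s.

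**5. A standard ANCOVA interval overstates the gain.** Taking arm means at the pooled baseline as if that baseline were fixed narrows the interval by 15% at ρ = 0.5 (0.461 to 0.392). It then covers the arm's population mean only 93.4% of the time (92.0% at ρ = 0.3).

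**The case against.** The strongest reply is that nothing is wrong with the plan's estimator. Protocol 6.2 sets a before-after aim with no control group. For that aim the mean paired change is unbiased, and its one-sample interval already includes chance baseline variation. This stands. A reader might infer that the raw changes are biased, or that drug effect and baseline imbalance are confounded within an arm; the documents do not support that. The imbalance is ordinary sampling error. It matters mainly when the two arms are compared by eye, which is why the 0.16 s figure applies to the gap between arms and only about half of it to one arm.

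A reader might also quote a gain in power. The plan contains no test, success rule, effect size or SD, so power has no counterpart in it. At ρ = 0.5, about 5 of the roughly 8 percentage points of narrowing come from the covariates and the rest from pooling.

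The case for the TG stratum is weaker than that for baseline %FMD. The plan does use the stratum in 7.1(3) and (4), and no benefit from adjusting for it can be calculated without an assumed effect.

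Finally, every subject has these covariates by design, but 7.1(5) foresees missing %FMD, and a central committee reviews the validity of the measurements (Protocol 11.1).

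**Conclusion.** The point holds as a modest loss of efficiency, not an error. Raw changes answer the stated question validly. An adjusted estimate would be between 0% and about 9% narrower from the covariates alone over ρ from 0.9 to 0.2, plus about 2 to 3% if a common variance is accepted. At ρ = 0.5 the chance imbalance in one arm, about 0.08 s, is small against a raw half-width of about 0.46 s; in the gap between arms it is about 0.16 s. All of this rests on an assumed ρ, equal SDs and 20 evaluable subjects per arm. If ρ is 0.7 or more there is little to gain. Adjustment would not remove time trends, or regression to the mean common to both arms. Priority is minor.

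**What to change.** Keep SAP 7.1(1) to (5) as they are. Add each arm's adjusted mean change in fasting %FMD at Weeks 4 and 8, with 95% intervals, from one constrained longitudinal model:
- %FMD at Visits 2, 3 and 4 as responses;
- one common Visit 2 mean, and arm-by-visit means afterwards;
- the allocation TG stratum as covariate;
- a stated small-sample method for the degrees of freedom.

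Name this model in SAP 10.1. That section still places the TG value at the start of treatment, whereas 7.1 and the version 4.0 revision entry place it in the Observation Period; use the latter. If ANCOVA is preferred, the SE of the arm means must allow for a random baseline.

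For 4-h postprandial %FMD use the same model with Visits 2 and 4 only, because that test is not done at Visit 3 (Protocol 9.3.3 and Appendix A; SAP 7.2).

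The cost is some SAP wording, one model and one table, with no new data, visits or patients. The downside is a common-variance assumption across arms, which the retained raw summaries let a reader check.

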7.2. Secondary Endpoints and the Analytical Methods

Analysis Set: Full Analysis Set

Analysis Variables: %FMD (4h postprandial)

TG level (fasting)

TG level (4h postprandial)

Plasma fatty acid fraction

Visit: Start of Treatment Period, Treatment Period 4 week and 8 week

* Treatment period 4 is excluded about %FMD (4h postprandial)

Stratification Factor: Fasting TG at Observation Period

[150<= - <200, 200<= - <500]

Analysis Methods: For the above analysis variables, the same analyses describes in

7.1 (1) - (4) are performed by visit.

7.3. Analysis of other endpoints

7.3.1. Efficacy Endpoints

Analysis Set: Full Analysis Set

Analysis Variables: Total cholesterol (fasting and 4h postprandial)

LDL-C(fasting and 4h postprandial)

HDL-C(fasting and 4h postprandial)

Remnant-like particle (RLP) cholesterol
(fasting and 4h postprandial)

Apoprotein B-48 (fasting and 4h postprandial)

C-reactive protein (CRP) (fasting)

8-epi-PGF2 α quantitative (urinary) (fasting)

Visit: Start of Treatment Period, Treatment Period 4 week and 8 week

Analysis Methods: For the above analysis variables, the same analyses describes in

7.1 (1) and (2) are performed by visit.

8. SAFETY EVALUATION

8.1. Frequency of Adverse Event Occurrence

8.1.1. Brief Summary of Adverse Events

Analysis Set: Safety Analysis Set

Analysis Variables: Adverse Event

Category Classification:

Causal Relationship with the Study Drug [Related, Unrelated]

Severity [Mild, Moderate, Severe]

Time of Onset [1<= - <29,
29<= - <57,

Analysis Methods: For the above analysis variables, the following analysis is performed for each treatment group.

- (1) Tabulation of frequencies of all adverse events
- (2) Tabulation of frequency of adverse events with a causal relationship to the study drug
- (3) Tabulation of frequency of all adverse events by severity
- (4) Tabulation of frequency of adverse events with a causal relationship to the study drug by severity
- (5) Tabulation of frequency of adverse events leading to study drug discontinuation
- (6) Tabulation of frequency of serious adverse events
- (7) Tabulation of frequency of Non-serious adverse events
- (8) Tabulation of frequency of serious adverse events with a causal relationship to the study drug
- (9) Tabulation of frequency of serious adverse events leading to study drug discontinuation
- (10) Tabulation of frequency of adverse events leading to death
- (11) Tabulation of frequency of all adverse events by time of onset

Incidence rates will be calculated as following on each analysis.

[Frequency of Subjects]

- Frequency by Severity

Subjects with one or more adverse events within a level of MedDRA term is counted only once in that level using the most severe incident. The denominator when calculating the incidence of adverse events is the number of subjects of safety analysis set.

- Frequency by Time of Onset

Subjects with one or more adverse events within a level of MedDRA term is counted only once in that category of time of onset. The denominator when calculating the incidence of adverse events is the number of subjects “whose study drug administration has been continued at that time point and later” or “who experienced an onset of adverse events at that time point or later” in safety analysis set and numerator is the number of subjects “experienced an onset of adverse events at that time point”.

- Analyses Other Than the Above

Subjects with one or more adverse events within a level of MedDRA term is counted only once for that MedDRA term. The denominator when calculating the incidence of adverse events is the number of subjects of safety analysis set.

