9.3.4 Completion (Visit 4) or discontinuation

1. Visit 4 shall be the last VISIT, and research subjects shall undergo the following tests at the designated medical institution for FMD measurement within the allowable range of Visit 4 (42 to 70 days after the study drug administration). If the study drug administration is discontinued, research subjects should, to the extent possible, undergo tests within 3 days from the last dose taken.
 - FMD test [fasting and 4-h postprandial (allowable range \pm 30 min)]
 - Laboratory tests [fasting and 4-h postprandial (allowable range \pm 30 min)]
 - Exploratory biomarker evaluation [fasting and 4-h postprandial (allowable range \pm 30 min)]

Food and drink consumption before the visit will be checked.

- Alcohol should not be consumed from 9:00 pm two days before the hospital visit to the time of visit and food should not be consumed from 9:00 pm on the day before to the time of visit.
 - Eating/drinking to excess and extreme change in dietary content should be avoided on the day before the hospital visit.
2. The principal investigator and the investigator shall perform the following tests, observations, and evaluations at Visit 4 (Day 42 to Day 70 days after the study drug administration). If the study drug administration is discontinued, research subjects should, to the extent possible, undergo tests, observations, and evaluations required for the last visit within 3 days from the last dose taken.
 - Physical examination
 - Vital signs
 - Concomitant drugs
 - Study drug compliance
 - Adverse Events

Since the principal investigator or the investigator is required to confirm safety of the tests, observations, and evaluations at Visit 4 or at discontinuation, FMD test and laboratory tests in (1) shall be performed first, and tests, observations, and evaluations in (2) shall be performed last.

At completion of the clinical research, the status of all research subjects administered the study drug shall be recorded on the CRF.

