10.2 Procedures

10.2.1 Collection and reporting of adverse events

10.2.1.1 Adverse event collection period

The collection of PTEs shall start after the acquisition of informed consent and continue until the start of the study drug administration at Visit 2 (Day -15 to Day -1 before the start of study drug administration). If withdrawal was decided before the start of administration of the study drug, the collection of PTEs shall be terminated at that point.

Collection of the adverse events shall commence at the start of administration of the study drug to research subjects [at Visit 2 (Day -15 to Day -1 before the start of study drug administration)] and continue until completion of the treatment period [Visit 4 (Week 8)] or at discontinuation.

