6.3.3. Study Medication Exposure

Analysis Set: All Subjects Administered

Analysis Variables: Duration of exposure (days)

[1<= - <29, 29<= - <57, 57<= - <=Max]

Analysis Methods: For the above analysis variables, the following analysis is performed for each treatment group and all subjects in the

analysis set.

- (1) Frequency count for discrete variables and summary statistics for continuous variables

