9. LISTING

Following lists will be create for randomized subjects.

- Demographics
- Discontinuation
- Protocol Deviation
- Subjects Excluded from Analyses

- Compliance of Study Drug Administration
- Adverse Event
- FMD Test
- Laboratory Tests (Blood biochemical examination including 4h postprandial)
- Laboratory Tests (Blood biochemical examination and urine test excluding 4h postprandial)

10. CONSIDERATIONS on STATISTICAL ANALYSIS

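### In the time-of-onset AE table, subjects off drug but still under AE collection enter the denominator only through an AE, so interval rates can be overstated and are never understated

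*SAP*

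**What the plan says.** SAP 8.1.1, under frequency by time of onset, builds the denominator from two groups within the Safety Analysis Set: subjects "whose study drug administration has been continued at that time point and later", or subjects "who experienced an onset of adverse events at that time point or later". The numerator is every subject with an onset at that time point. SAP 8.1.2 repeats the rule for the tables by SOC and PT. The onset intervals, as listed in 8.1.2, are Day 1–28, Day 29–56 and Day 57 onward.

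On dosing and observation:

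- Protocol 6.1: "The duration of the treatment period is 8 weeks". Appendix A calls the first medication day Day 1, so a nominal course ends on Day 56.
- Protocol 6.1 also has visits running "to completion of study drug administration [Visit 4 (Week 8".
- Protocol 10.2.1.1: AE collection is to "continue until completion of the treatment period [Visit 4 (Week 8)] or at discontinuation".
- Protocol 9.3.4 sets the window as "Visit 4 (42 to 70 days after the study drug administration". The site examination, including the AE check, is done last. Under Protocol 6.1 it may be a separate visit from the FMD test.
- Protocol 9.3.4 and Appendix A: subjects who stop early are to be examined within 3 days of the last dose, where possible.

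**The concern.** AE collection ends at Visit 4 or the discontinuation visit, not at the last dose, so a subject can be off drug and still observed in an interval. Suppose two subjects both take their last dose on Day 56 and both have Visit 4 after Day 57. If one reports an AE on Day 57 and the other reports nothing, the first enters the Day 57+ denominator and the second does not. Off-drug subjects in that last column have 100% incidence by construction.

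This is the SAP's only tabulation of AEs by onset time. Its purpose is to show when events occur, and a denominator that depends on the outcome makes the interval rates hard to read. With about 20 subjects per arm, leaving out one or two event-free subjects changes the printed percentage.

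**Working it through.** The documents give no AE rate, no interval denominator and no count of subjects off drug but under collection. There is therefore no stated figure to reproduce. I read the time point as the first day of the interval.

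**Direction.** For one interval, let K be the subjects on drug and M those off drug but under AE collection. Let a and b be the on-drug and off-drug subjects with an onset in the interval. Let c be the off-drug subjects whose only onset is in a later interval.

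- SAP rate = (a + b) / (K + b + c)
- Rate among subjects observed = (a + b) / (K + M)

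Since b + c cannot exceed M, the SAP rate is never the lower of the two. They are equal if M = 0, if every off-drug subject has an AE in that or a later interval, or if there are no AEs in the interval.

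**Where it can arise.**

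- Day 1–28: every Safety Analysis Set subject is dosed on Day 1, so all are counted and there is no effect.
- Day 29–56: it needs a last dose before Day 29 and AE collection continuing on or after Day 29. Off-drug subjects with only a later AE (c) also enter, which narrows the gap but cannot reverse it.
- Day 57+: it needs a last dose before Day 57 and collection on or after Day 57. Examples are a last dose on Day 56 with Visit 4 on Day 57–70, or a discontinuer with a last dose on Day 54–56 seen on Day 57–59. Subjects dosed on Day 57 or later are already counted, and subjects last seen before Day 57 play no part. Here c = 0.

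**Worked count (assumed).** Take 20 observed after Day 56, of whom 18 are on drug and 2 off, with 2 AEs. If both AEs are on drug, the SAP gives 2/18 = 11.1%. With one in each group it gives 2/19 = 10.5%. Among all observed the rate is 2/20 = 10.0%.

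**Expected size in the last interval.** Assume N subjects observed, one of them off drug, and the same AE risk p on and off drug. With n = N − 1, the expected SAP rate is 1 − n(1 − p)·[(1 − p)/n + p/N], which simplifies to p + p(1 − p)/N. The overstatement is therefore p(1 − p)/N:

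| N observed | p = 5% | p = 10% |
|---|---|---|
| 10 | 0.0475/10 = 0.48 points (5.5%) | 0.09/10 = 0.90 points (10.9%) |
| 20 | 0.0475/20 = 0.24 points (5.2%) | 0.09/20 = 0.45 points (10.5%) |

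N, p and the single off-drug subject are assumptions.

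**The case against.** The strongest reply is that the triggering situation may hardly occur. Protocol 6.1 ties completion of dosing to Visit 4, and Protocol 10.2.1.1 equates the end of the treatment period with Visit 4. Protocol 8.1.1 has the visit-day dose taken after the tests. SAP 6.3.3 uses exposure classes "1<= - <29, 29<= - <57, 57<= - <=Max", which foresee 57 days or more. On that reading, dosing and AE collection end together for completers and the effect is zero. This stands for many subjects. It does not remove the cases where dosing stops at a nominal Day 56, where the final examination falls on a later day than the last dose, or where an early stopper is seen in the next interval.

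The second limb also has a purpose: it keeps every numerator subject in the denominator. That is true, but it does so by selecting on the outcome. A denominator of everyone under collection, with later events listed separately, avoids that.

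It can also be said that truncation of the last interval by Visit 4 distorts the late rate more than this rule does. That is probably right, and it applies to the SAP rule and to the replacement alike.

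Three stronger readings might be inferred, and the documents support none of them:

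- **The late AE rates are materially inflated.** That would need a large share of those observed after Day 56 to be off drug, and no section indicates it.
- **The Day 29–56 effect is known to be small.** The 3-day examination is only to the extent possible and no dropout figure is given, so no bound can be stated.
- **The two dose arms are distorted differently.** Nothing shows this.

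**Conclusion.** The rule as written is outcome-dependent, and the direction of its error is certain: the interval rate is never below the rate among subjects observed, and it can be above it. Whether this happens in the data, and how often, cannot be told from the documents. The size is zero if dosing runs to Visit 4. Otherwise, one off-drug subject in the last interval adds roughly 0.25–0.9 percentage points under the stated assumptions.

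The consequence is limited. Only item (11) in SAP 8.1.1 and 8.1.2 is affected. All other AE tables use the full Safety Analysis Set, and no test or stopping rule uses this table. SAP 9 provides for case-level checks: "Following lists will be create for randomized subjects", including AEs and discontinuations. This is a conditional weakness of the rule and not a demonstrated error in results. It is worth correcting because the correction is cheap.

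**What to change.** In SAP 8.1.1 and 8.1.2, item (11):

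- Denominator for each interval: all Safety Analysis Set subjects still under AE collection on its first day, meaning Visit 4 or the discontinuation visit falls on or after that day, regardless of dosing or AE status.
- Numerator: those of them with an onset in the interval.
- List separately any AE with onset after collection nominally ended.
- Footnote that the last interval is short and truncated by Visit 4, so its crude rate should not be compared directly with the two 28-day intervals.

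The cost is a sentence in each of two sections, a footnote and a small programming change, using dates already collected.

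The downside is dilution: subjects observed for only part of the last interval count as fully at risk. To show the scale, assume Visit 4 spread evenly over Day 57–70 and a constant hazard of 20% per 28 days. The daily risk is then h = 1 − 0.8^(1/28) = 0.00794. The crude late rate is the mean of 1 − (1 − h)^d over d = 1 to 14, about 5.8%. A full 14 days would give 1 − 0.8^(14/28) = 10.6%. At a risk of 5.8%, the overstatement under the present rule with one off-drug subject among 10 is 0.058 × 0.942/10, about 0.5 points. The footnote is therefore as necessary as the new denominator.
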